### **13.1 SAFETY INSTRUCTIONS**

Specific instructions concerning safety management by the treating physician should be developed here, e.g., management of abnormal laboratory values, reporting of outcome events as SAE or not, etc.

All events will be managed and reported in compliance with all applicable regulations.

#### **13.1.1 Definitions of AE and SAE**

An AE is any untoward medical occurrence in a patient or clinical investigation patient administered a pharmaceutical product and which does not necessarily have to have a causal relationship with a treatment.

A SAE is any untoward medical occurrence that at any dose:

- Results in death or;
- Is life-threatening or;  
*Note: The term "life-threatening" in the definition of "serious" refers to an event in which the patient was at risk of death at the time of the event; it does not refer to an event which hypothetically might have caused death if it were more severe.*
- Requires inpatient hospitalization or prolongation of existing hospitalization or;
- Results in persistent or significant disability/incapacity or;
- Is a congenital anomaly/birth defect;
- Is a medically important event:

Suspected transmission of infectious agent; is any suspected transmission of an infectious agent via a medicinal product (e.g., product contamination);

- Required Intervention to Prevent Permanent Impairment or Damage (Devices).

If you believe the intervention was necessary to preclude permanent impairment of a body function, or prevent permanent damage to a body structure, either situation suspected to be due to the use of a medical product (This criterion should be added if a specific device is used

Medical and scientific judgment should be exercised in deciding whether expedited reporting is appropriate in other situations, such as important medical events that may not be immediately life-threatening or result in death or hospitalization but may jeopardize the patient or may require intervention to prevent one of the other outcomes listed in the definition above.

### **13.1.2 Collection of overdose and pregnancy**

Overdose: Any case of accidental or intentional overdose, even in the absence of an AE (asymptomatic), is to be reported to PV Sanofi or responsible Vendor (within 24 hours of awareness, no later than the following working day) and recorded accordingly on the corresponding page(s) of in the CRF as explained below. In case of overdose the patient should remain under observation for as long as it is considered appropriate by the treating physician. Appropriate symptomatic measures should be taken.

Pregnancy: Pregnancy occurring in the patient or the female partner of a male patient exposed to a Sanofi drug must be reported to PV Sanofi or responsible Vendor (within 24 hours of awareness, no later than the following working day) and recorded immediately on the corresponding page(s) of in the CRF as explained below.

### **13.1.3 Obligations of the physician regarding safety reporting**

All AE regardless of relationship to Cemiplimab or any other product of the Sanofi group, spanning from the signature of the ICF form until the end of the study as defined by the protocol for each patient, are to be recorded immediately (SAE within 24 hours of awareness, no later than the following working day, non serious AE no later than within 30 d of awareness) for all AEs on the corresponding page(s) of the paper CRF or e-CRF as explained below.

AE reporting to *Alcedis GmbH*

- SAE

In case of paper CRF:

In the case of any AE the treating physician must immediately:

- SEND (within 24 hours, no later than the following working day, preferably by fax) the signed and dated corresponding page(s) in the CRF to *Alcedis GmbH* whose name, address and fax number appear on the third page of this Protocol;
- ATTACH the photocopy of all examinations carried out and the dates on which these examinations were performed. Care should be taken to ensure that the patient's identity is protected and the patient's identifiers in the study are properly mentioned on any copy of source document provided to *Alcedis GmbH* for laboratory results, include the laboratory normal ranges;

All further documentation should be sent to *Alcedis GmbH* within 24 hours of knowledge, no later than the following working day. In addition, any effort should be made to further document each SAE that is fatal or life threatening within the week (7 days) following initial notification.

In case of e-CRF:

- ENTER (within 24 hours, no later than the following working day) the information related to the AE/SAE in the appropriate screens of the e-CRF; the system will automatically send the notification to the representative of *Alcedis GmbH* after approval of the treating physician within the e-CRF or automatically after a pre-set delay.
- SEND (preferably by e-mail) the photocopy of all examinations carried out and the dates on which these examinations were performed, to *Alcedis GmbH* whose name, email address appear on the first page of this Protocol. Care should be taken to ensure that the patient's identity is protected and the patient's identifiers in the Study are properly mentioned on any copy of source document provided to *Alcedis GmbH*. For laboratory results, include the laboratory normal ranges
- All further data updates should be recorded in the e-CRF as appropriate, and further documentation as well as additional information (for Lab data, concomitant Medication, patient status ...) should be sent (by e-mail) to *Alcedis GmbH* within 24 hours of knowledge, no later than the following working day, . In addition, any effort should be made to further document each Serious AE

that is fatal or life threatening within the week (7 days) following initial notification.

A back-up plan is used (using paper flow) in case the e-CRF system does not work.

- Non-serious AE

In case of e-CRF:

- ENTER (no later than within 30 days of awareness) the information related to the AE in the appropriate screens of the e-CRF; the system will automatically send the notification to *Alcedis GmbH* after approval of the treating physician within the e-CRF or automatically after a pre-set delay.

In case of paper CRF:

- SEND (no later than within 30 days of awareness) the signed and dated corresponding page(s) in the CRF to *Alcedis GmbH* representative whose name, address appear on the second page of this protocol.

### 13.2 SAFETY OBSERVATIONS

- The treating physician should take all appropriate measures to ensure the safety of the patients as per normal practice.
- In case of any AE, the patient must be followed up until clinical recovery is complete and laboratory results have returned to normal, or until progression has been stabilized. This may imply that follow-up will continue after the patient has left the study.
- In case of any AE brought to the attention of the treating physician at any time after cessation of Cemiplimab, and considered by him/her to be caused by Cemiplimab with a reasonable possibility, this should be reported to the *Alcedis GmbH*.

### 13.3 AE OF SPECIAL INTEREST (AESI)

An AE of special interest (serious or non-serious) is one of scientific and medical concern specific to the product or program, for which ongoing monitoring and rapid communication by the treating physician to *Alcedis GmbH* is required. Such AE normally require thorough documentation and investigation to characterize them.

In the event of an AESI, *Alcedis GmbH* will be informed immediately (i.e., within 24 hours, no later than the following working day) even not fulfilling a seriousness criterion, using the specific AESI form as appropriate.

The protocol defines a specific subset of AESIs and laboratory abnormalities that must be immediately reported, even if not fulfilling seriousness criteria. The following events

must be systematically reported by the treating physician as AESIs with immediate notification for all studies:

- Immune related reactions (ir-ARs) including immune-related pneumonitis, colitis, hepatitis, endocrinopathies, immune-related skin adverse reactions, nephritis, and irARs in other organs.
  - *Since Clinical manifestations of irARs are generally autoimmune-like, any AEs considered as irARs with no clear alternative etiology will need to be reported.*

**Note: for each immune related reaction the Targeted follow-up form has to be fulfilled in addition to the standard AE form.**

- Infusion related reactions (IRRs)
  - *Cases with AEs coded to infusion related reaction, hypersensitivity, type hypersensitivity, drug hypersensitivity and severe or life-threatening infusion- related reactions, including bronchospasm, anaphylaxis, anaphylactic reaction, anaphylactic shock, anaphylactoid reaction, anaphylactoid shock, angioedema, and severe hypotension, during or immediately following the initial infusion, need to be reported.*

**Note: for each infusion related reaction the Targeted follow-up form has to be fulfilled in addition to the standard AE form.**

- Pregnancy of female subject entered in a study (as well as pregnancy occurring in a female partner of a male subject entered in a study with Sanofi product);
- Pregnancy of a female exposed to a Sanofi product (as well as pregnancy occurring in a female partner of a male exposed to a Sanofi product) will be reported to the CRO *Alcedis GmbH*. It will be qualified as a SAE (only if it fulfills one of the seriousness criteria).

A pregnancy data collection form will be provided to the treating physician to ensure collection of additional information regarding the outcome of the pregnancy. If the exposed female refuses to provide any information regarding the pregnancy and its outcome, this information will be captured on the Sanofi Pregnancy/Drug Exposure via pregnancy data collection form.

- Symptomatic overdose (serious or non-serious) with Sanofi product (overdose of the studied product(s) to be defined here.)

#### **13.4 OBLIGATIONS OF *ALCEDIS GMBH***

During the course of the study, the *Alcedis GmbH* will report to the appropriate Health Authorities and IECs/IRBs all cases that meet expedited reporting criteria in accordance with all local and global regulations

The Sponsor will report all safety observations made during the conduct of the study in the study report.

## 14 STATISTICAL CONSIDERATIONS

### 14.1 DETERMINATION OF SAMPLE SIZE

#### Sample size justification

The primary objective of the study is to describe TTNT or death in patients with advCSCC initially treated with Cemiplimab (prospective cohort) or other therapeutic approaches (retrospective cohort). The sample size is justified based on the precision (half-length of 95%-CI) of median TTNT. Based on the results presented for TTNT in (Ludwig et al, 2015) it is expected, that with 200 patients median TTNT can be estimated with a precision of 10%.

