
STATISTICAL METHODOLOGY
	
Sample size justification
 
The primary objective of the study is to describe TTNT or death in 200 patients with advCSCC initially treated with Cemiplimab (prospective cohort) or 200 patients with other therapeutic approaches (retrospective cohort).
 
  
 Sample size	Number of event	Width of 95%CI	Median TTNT (months)	Lower limit 95% CI	Upper limit 95% CI	
   
 200	180	8.9	30.0	26.1	34.9	
 
 11.8	40.0	34.7	46.6	
 
 14.8	50.0	43.4	58.2	
  
 
References Mathews, Paul. 2010. Sample Size Calculations: Practical Methods for Engineers and Scientists. Mathews Malnar and Bailey, Inc.
 
Including 200 patients in each cohort produces a two-sided 95% confidence interval with a width equal from 8.9 to 14.8 when the expected median TTNT is respectively from 30 to 50 monts. The percent censoring is anticipated to be 10%.
 
Primary analysis
 
The primary analysis is descriptive. TTNT will be estimated and visualized for each cohort separately by Kaplan-Meier estimators. Median TTNT will be presented with 95%-confidence intervals. Potential predictors of TTNT will be analyzed using Cox proportional hazards regression.
 
Secondary analysis
 
All secondary outcomes will be analyzed descriptively.
 
The rate of ORR and 95%-CI will be given for each cohort. In addition
	Sample size	Number of event	Width of 95%CI	Median TTNT (months)	Lower limit 95% CI	Upper limit 95% CI	200	180	8.9	30.0	26.1	34.9	11.8	40.0	34.7	46.6	14.8	50.0	43.4	58.2
Sample size	Number of event	Width of 95%CI	Median TTNT (months)	Lower limit 95% CI	Upper limit 95% CI																
200	180	8.9	30.0	26.1	34.9																
		11.8	40.0	34.7	46.6																
		14.8	50.0	43.4	58.2																

	
and in an exploratory way, the pooled rate and its 95%-confidence interval will also be given. Potential predictors of response will be analyzed using logistic regression and/or Factorial Multiple Correspondences Analyses.
 
For time to event endpoints, Kaplan-Meier curves will be presented and median time to event will be estimated with corresponding 95%-confidence intervals.

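### Section 14.1 claims 10% precision for the median TTNT with 200 patients, but the synopsis table for the same 200 patients implies about 15%

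*Protocol*

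**What the plan says.** The protocol justifies the sample size in two places.

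Section 14.1 sets the metric: "The sample size is justified based on the precision (half-length of 95%-CI) of median TTNT". It then cites the TTNT results of a multiple myeloma trial and expects that "with 200 patients median TTNT can be estimated with a precision of 10" per cent. It gives no median, event count, censoring rate or survival model.

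The synopsis (Statistical methodology) says: "Including 200 patients in each cohort produces a two-sided 95% confidence interval with a width equal from 8.9 to 14.8". These widths are in months and belong to assumed medians between 30 and 50 months. On censoring, the synopsis adds: "The percent censoring is anticipated to be 10" per cent, which is 180 events in 200 patients. Its table, read as width, median, lower limit and upper limit in months, has the rows "8.9 30.0 26.1 34.9", "11.8 40.0 34.7 46.6" and "14.8 50.0 43.4 58.2".

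Section 8.1 says that the study is descriptive and tests no prior hypothesis, and refers to the synopsis for the detailed justification.

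**The concern.** Both statements concern the same endpoint, the same 200 patients per cohort and the same 95% level. One expresses precision as a percentage of the median and the other as a full width in months, so the mismatch is easy to miss. Put on one scale, they disagree: the half-length implied by the table is about 48% larger than the one stated (14.8/10 = 1.48).

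Because no hypothesis is tested, the precision of the median TTNT is the only quantitative property offered in support of 200 patients per cohort. Someone who reads only the statistical section is told that the study will be more precise than the protocol's own table indicates.

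**Working it through.** **Inputs.** From the synopsis: 200 patients per cohort, 10% censoring, 180 events, two-sided 95% interval, medians of 30, 40 and 50 months. From section 14.1: precision is the half-length of the 95% interval, claimed to be 10%. From sections 7.1 and 7.2: prospective follow-up is 36 months.

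**Step 1: reproduce the synopsis table.** For exponential times with d events and median m, the exact limits are m·2d/χ²(0.975; 2d) and m·2d/χ²(0.025; 2d). With d = 180 the multipliers of m are 0.8686 and 1.1638.

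| Median | Recomputed limits | Recomputed width | Printed limits | Printed width |
|---|---|---|---|---|
| 30 | 26.06 to 34.91 | 8.86 | 26.1 to 34.9 | 8.9 |
| 40 | 34.74 to 46.55 | 11.81 | 34.7 to 46.6 | 11.8 |
| 50 | 43.43 to 58.19 | 14.76 | 43.4 to 58.2 | 14.8 |

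Every printed value agrees after rounding, so the synopsis figures are those of an exponential model with 180 events.

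**Step 2: convert to the metric of section 14.1.** Half-length over median, from the printed widths:

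- 8.9/2 = 4.45; 4.45/30 = 14.8%
- 11.8/2 = 5.9; 5.9/40 = 14.75%
- 14.8/2 = 7.4; 7.4/50 = 14.8%

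Without rounding, (1.1638 − 0.8686)/2 = 14.76% for any median.

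**Step 3: look for a reading that gives 10%.**

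- No censoring, 200 events, same formula: 14.0%.
- Simple Wald approximation, 1.96/√d: 14.6% with 180 events and 13.9% with 200.
- Shorter (lower) arm of the interval alone, 180 events: 1 − 0.8686 = 13.1%.
- Lower confidence level, 180 events: 12.4% at 90% and 9.6% at 80%. Only the 80% interval falls below 10%, and section 14.1 specifies 95%.
- Non-parametric Kaplan-Meier median under an exponential curve, 1.96/(√n·ln 2): 21.1% with n = 180 and 20.0% with n = 200, so further away.

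**Step 4: events needed for 10%.** By the exact exponential formula the half-length first reaches 10% at 388 events. At 10% censoring that is 388/0.9 = 431.1, so 432 patients per cohort.

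**Step 5: how far 15% depends on 180 events.** In the prospective cohort, with 36 months of follow-up, no other loss and exponential times, the event probability is 1 − 2^(−36/m).

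| Median | Event probability | Events in 200 | Half-length |
|---|---|---|---|
| 30 | 0.565 | about 113 | 18.7% |
| 40 | 0.464 | about 93 | 20.8% |
| 50 | 0.393 | about 79 | 22.6% |

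Medians of 40 and 50 months also lie beyond the end of follow-up, so these two half-lengths rest on the parametric model.

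**The case against.** **The 10% may rest on another model.** Section 14.1 names no exponential model and points to an outside trial whose TTNT figures the protocol does not give. Relative precision depends on the shape of the curve: for a Weibull distribution with known shape k the half-length is about 1.96/(k·√180), and k of about 1.46 gives 10%. This stands. A reader might infer that 10% is unattainable with 200 patients, and the documents do not support that. They show only that 10% disagrees with the synopsis calculation and comes without inputs. The figure of 388 events has the same limit.

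**The table prints no percentage.** Also correct. The 14.8% is derived here. It happens to share its digits with the printed 14.8, which is a full width in months at a median of 50. The two should not be confused.

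**The effect is small.** Section 8.1 already directs the reader to the synopsis, whose table is correct on its own assumptions. Section 14.3.2.1 will report the observed Kaplan-Meier median and its interval whatever was planned. Patient numbers, endpoint and analysis do not change. This limits the severity but leaves the contradiction in place. Nor is it a detail left to a statistical analysis plan, because the protocol itself states both figures.

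**Conclusion.** The inconsistency is real. Section 14.1 states a half-length of 10% of the median; the synopsis table implies about 15% for the same 200 patients with 180 events. That 15% assumes exponential times and 180 events. Under that model 10% is not reached even with 200 events, and section 14.1 offers nothing else to support it.

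A reader might go on to infer that the study is too small or has lost power. The documents do not support that: no hypothesis is tested and no required precision is set that 200 patients would fail to meet. The error lies in what the protocol promises about precision. It should be fixed, but it does not undermine the design.

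The 15% should not be treated as secure for the prospective cohort either. It needs 180 events, and 36 months of follow-up under the table's own medians gives about 113, 93 and 79, with half-lengths of about 19%, 21% and 23%.

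**What to change.** Delete the 10% sentence in section 14.1 and refer to a single justification, expressed in the same metric in section 14.1 and the synopsis and with its assumptions written out. For example: with 200 patients per cohort and 180 events, the half-length of the 95% interval for the median TTNT is about 15% of the median under an exponential model.

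Add that this depends on 180 events occurring. For the prospective cohort, give the figures for follow-up ending at 36 months: about 113, 93 and 79 events and half-lengths of about 19%, 21% and 23% at exponential medians of 30, 40 and 50 months, with no other loss.

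Keep 200 patients per cohort. The cost is a few lines of text and a less favourable stated precision; no patients, visits or analyses are added.

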### 14.2 ANALYSIS POPULATION

All eligible patients will be analyzed

### 14.3 STATISTICAL METHODS

#### 14.3.1 Analyses variables

##### **14.3.1.1 Primary variable**

The TTNT defined as time from start of Cemiplimab treatment to the start of next systemic therapy or death outside BSC. All next systemic treatments excluding BSC will be evaluated.

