## 1 SYNOPSIS

COMPOUND: Cemiplimab (SAR439684)	
STUDY No: OBS16381	
TITLE	Two cohort registry study for patients with advanced CSCC treated with Cemiplimab or other approaches
LOCATION	Approx. 60 sites in Germany, plus 5 sites in Switzerland and 5 sites in Austria
SCIENTIFIC COMMITTEE CHAIR PERSON	[REDACTED]
STUDY OBJECTIVE(S)	
The objectives of the study are
 
Prospective cohort:
 

• To identify TTNT

• To identify potential determinants of disease progression as final outcome, Quality of life (QoL), pain and other health related outcomes for CSCC patients undergoing treatment with Cemiplimab

• To collect long-term effectiveness and describe effects of treatment

• To collect safety data in a real world setting

 
Retrospective cohort:
 

• To examine real-world data of advanced CSCC (advCSCC) patients who were treated before approval of Cemiplimab (treatment approaches, safety, patient characteristics, long-term effects)

 
Primary objective prospective and retrospective cohort:
 
Primary objective for this non-interventional study (NIS) is time to next treatment (TTNT) excluding best supportive care (BSC).
 
Secondary objectives prospective cohort:
 
Patient demographics and baseline characteristics (TNM stage), Cemiplimab treatment regimen, duration of treatment (DOT), prior and post Cemiplimab treatments, response to Cemiplimab treatment (ORR, CR, PR, SD), duration of response (DOR), disease control rate (DCR = CR+PR+SD), time to treatment failure (TTFT), overall survival (OS), progression free survival (PFS), safety data, quality of Life (QoL) incl. pain.
 
Secondary objectives retrospective cohort:
 
Patient demographics and baseline characteristics (TNM stage), effectiveness (ORR, PFS, OS) and safety of different treatment options used routinely for advanced CSCC prior to Cemiplimab launch, patterns

	of treatment.

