#### **Informed Consent Form (ICF)**

It is the responsibility of the physician or designee to obtain written ICF from each compliant patient of the prospective cohort prior to the documentation of his / her data in the eCRF. One original ICF must be retained by the study site as part of the patient's study record, and another original of the signed ICF must be given to the patient. The ICF must be provided before the patients data are documented in the eCRF.

Enrolled patients who initiate treatment with Cemiplimab will complete baseline QoL assessments at the time of ICF, and will continue with subsequent assessments at their Cemiplimab dosing and advCSCC standard of care (SoC) visits for up to 3 years. Additional procedures will be performed as dictated by the local SoC, as deemed necessary by the treating physician based on usual care. Data collection will mirror SoC procedures relating to the patient's treatment. Patients will remain eligible and will be encouraged to stay in the study if they discontinue Cemiplimab (permanently or temporarily). Once enrolled, patients will remain in the study until further participation is declined.

In the study the data to support the primary objectives are abstracted from medical records for patients with advCSCC (ladvCSCC or mCSCC), living or deceased, from the time of advCSCC diagnosis (i.e., index date) until the most recently documented visit, death, or lost to follow up whichever comes later. Specifically, data on treatment patterns prior to date of first mCSCC or ladvCSCC diagnosis, as far as data permits will be collected to support the secondary objectives.

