## **7.2 DURATION OF STUDY PARTICIPATION FOR EACH PATIENT**

In the prospective cohort the data will be recorded during a follow-up of 36 months, beginning after study inclusion.

In the retrospective cohort we will document at one time point patients not intended for Cemiplimab therapy, who were first diagnosed advCSCC between Jan/2012 and Aug/2019. QoL data will be collected from patients within the prospective cohort. It is planned to perform yearly interim analyses and a final report at the end of the study.

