### 8.2 INCLUSION CRITERIA

Prospective cohort:

- Planned treatment for advCSCC adult patients  $\geq 18$  yrs who are at the first time initiated on Cemiplimab treatment according to SmPC of Cemiplimab
- Able to understand and complete study-related questionnaires
- Signed ICF

Retrospective cohort:

- Patients  $\geq$  18 years with advCSCC first diagnosed between Jan/2012 and Aug/2019
- From these patients only anonymous data will be collected. Thus no Sanofi-ICF is needed. This procedure allows including data from patients who are no longer alive (planned).

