### PARAMETER AND DEFINITIONS for the CRF's

Outcome(s)	Specific parameter	Definition	Record in Visit (month)
Clinical outcomes	Mortality, all cause, advCSCC related, and date of death	Defined as death due to all cause or disease related	-
	OS from diagnosis	Defined as time from 1 st Cemiplimab treatment until death from any cause, censoring for date of most recent follow-up in surviving patients	-
	Progression	Defined as documented in medical records	3,6,9,12,18,24,36
	Date of progression	Defined as date of first documented progression in the medical record	3,6,9,12,18,24,36
	Time to next treatment (TTNT)	Defined as time from start of Cemiplimab treatment to the start of next systemic therapy or death	-
	PFS	Defined as documented start of systemic Cemiplimab therapy until disease progression or death	3,6,9,12,18,24,36
	Patient		male / female

characteristics	Gender		
	Nationality		Baseline
	Year of birth		Baseline
	Skin phototype	Defined as Type 1, 2.....6	Baseline
	Informed consent		Baseline
	Comorbidities	Auto-immune-disease, hematologic disease, severe cognitive impairment, etc.	Baseline and 3,6,9,12,18,24,and 36
	Quality of life data (QoL)	Questionnaire: EORTC – QoL Core 30	Baseline and 3,6,9,12,18,24,and 36
	Pain	Questionnaire: EORTC – QoL Core 30	Baseline and 3,6,9,12,18,24,and 36
	Adverse events (AE) Quality of life data Reasons for discontinuing therapy Frequency of administration	Defined event as yes/no (specify, related/unrelated to anticancer therapy, serious/non-serious as documented in medical records NOTE: We will limit data collection to Common Terminology Criteria for AE (CTCAE)5.0 as documented in the medical record.Questionnaire: EORTC – QoL Core 30  Defined as lack of response, disease progression, toxicities, side effects, therapy completion, patient decision, death, other (specify) Defined as every day (QD), twice a day (BID), every week (QW), every other week (Q2W), every three weeks (Q3W), every four weeks (Q4W), other	Baseline and 3,6,9,12,18,24,and 36
	Adverse events (AE)	Defined event as yes/no (specify, related/unrelated to anticancer therapy, serious/non-serious as documented in medical records NOTE: We will limit data collection to Common Terminology Criteria for AE (CTCAE) 5.0 as documented in the medical record.	Baseline and 3,6,9,12,18, 24,36
Lab results	Lab parameter LDH		Baseline
Status	Date of physical check-up		Status at Baseline

	Organ transplantation		

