#### **14.3.1.3 Secondary variables of the retrospective cohort**

- \* Characteristics of retrospective patient population, patterns of care and effectiveness of different treatment options used under routine conditions for advanced CSCC prior to Cemiplimab launch
- \* Safety data on study participants
- \* Proportion of patients surviving at month 3, 6, 9, 12, 18, 24 and up to months 36 from initiation of systemic therapy
- \* PFS defined as time from first documented systemic therapy initiation until progression or treatment discontinuation due death or end of follow up
- \* Patient demographics and baseline characteristics (incl. age, performance status etc.) at study entry
- \* TNM stage (AJCC or UICC)
- \* Patterns of treatment for the retrospective cohort.

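### The primary variable TTNT is defined only from the start of cemiplimab, so it has no time zero in the retrospective cohort, where it is also primary

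*Protocol*

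**What the plan says.** **TTNT is primary in both cohorts.** Under a Synopsis heading that names both cohorts: "Primary objective for this non-interventional study (NIS) is time to next treatment (TTNT) excluding best supportive care (BSC"). Sections 6 and 14.1 repeat this, and 14.3.2.1 asks for a separate Kaplan-Meier estimate and a median with 95% CI in each cohort.

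**It is defined twice, with the same start.** Section 14.3.1.1: "The TTNT defined as time from start of Cemiplimab treatment", ending at the next systemic therapy or death. CRF table in Section 9: "Defined as time from start of Cemiplimab treatment to the start of next systemic therapy or death". Section 11.2, which covers both cohorts, refers back to that table. Neither place gives a retrospective version.

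**The retrospective cohort is not a cemiplimab cohort.** The Synopsis describes it as receiving other therapeutic approaches. Section 7.2 says "we will document at one time point patients not intended for Cemiplimab therapy", and the Synopsis has similar wording. The inclusion criterion in 8.2 is adults "with advCSCC first diagnosed between Jan/2012 and Aug/2019". Neither 8.2 nor 8.3 requires any systemic therapy, and 14.2 analyses every eligible patient.

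**PFS was adapted to this cohort.** Section 14.3.1.3: "PFS defined as time from first documented systemic therapy initiation until progression".

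**Precision.** The Synopsis table assumes 200 patients, 180 events and 10% censoring, and is stated for each cohort.

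**The concern.** A time-to-event variable needs a start that every analysed patient has. Here the stated start is an exposure that one of the two cohorts is, by description, not meant to have. The SAP could not simply add detail, because it would have to replace an explicit protocol definition of the primary variable.

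Three things are at stake:

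- Half of the planned primary analysis cannot be produced as written.
- If the start is chosen after the records have been abstracted, the retrospective median depends on a choice made with the data in hand.
- Any start tied to systemic therapy leaves patients who had only surgery or radiotherapy without a time zero, so fewer than 200 may contribute and the stated precision would not apply.

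**Working it through.** **1. The definitions against the cohort.**

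| Item | Prospective | Retrospective |
|---|---|---|
| TTNT is primary (Synopsis, 6, 14.1, 14.3.2.1) | yes | yes |
| TTNT start (14.3.1.1; CRF table) | start of cemiplimab | none stated |
| PFS start (14.3.1.2; 14.3.1.3) | first cemiplimab | first documented systemic therapy |
| Systemic therapy needed for eligibility (8.2, 8.3) | yes, cemiplimab | no |

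Retrospective patients never given cemiplimab contribute 0 TTNT times. The formal criteria do not rule out later cemiplimab. Any patient who did receive it would be timed from a drug that this cohort is not meant to describe.

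**2. The protocol's precision table.** Inputs from the Synopsis: d = 180 events and median m = 30, 40 or 50 months. For an exponential model with exact chi-square limits:

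lower = 2dm / χ²(0.975; 2d), upper = 2dm / χ²(0.025; 2d)

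With 2d = 360 the quantiles are 414.46 and 309.33. For m = 30, 10,800/414.46 = 26.06 and 10,800/309.33 = 34.91.

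| Median | Computed CI (width) | Stated CI (width) |
|---|---|---|
| 30 | 26.06–34.91 (8.86) | 26.1–34.9 (8.9) |
| 40 | 34.74–46.55 (11.81) | 34.7–46.6 (11.8) |
| 50 | 43.43–58.19 (14.76) | 43.4–58.2 (14.8) |

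The table reproduces to rounding. It therefore needs 180 timed events in the retrospective cohort, which the present definition cannot supply.

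**3. Precision if the start is first systemic therapy.** The protocol does not give the share of retrospective patients who had systemic therapy, so the shares below are assumptions. Events = 200 × share × 0.90, with the same formula.

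| Share treated (assumed) | Events | Width at median 30 | Width at median 50 |
|---|---|---|---|
| 100% | 180 | 8.9 | 14.8 |
| 75% | 135 | 10.3 | 17.1 |
| 50% | 90 | 12.7 | 21.1 |
| 25% | 45 | 18.3 | 30.5 |

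**4. Why the start must be fixed in advance.** Suppose the clock ran from diagnosis, with a constant time g from diagnosis to first systemic therapy. The median then moves by g: 30 + 3 = 33, 30 + 6 = 36 and 30 + 12 = 42 months. The values of g are assumptions, since the protocol gives none. The half-width in the stated table at a 30-month median is 8.86/2 = 4.4 months, so a lag of 6 months would already move the estimate by more than its planned precision.

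**5. The selection wording.** The Synopsis and 7.2 describe retrospective patients as not intended for cemiplimab. The criteria in the Synopsis, 8.2 and 8.3 contain no such rule, and nothing says when intention is judged. Take a patient diagnosed in 2018, given another systemic therapy, and first started on cemiplimab after enrolment opened in March 2021. That patient could meet the 8.2 criteria of both cohorts. Because retrospective data are anonymous, a duplicate might not be noticed.

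**The case against.** The strongest defence is that the intention is easy to guess. The retrospective outcomes with a stated origin, PFS and the survival proportions, run from the start of systemic therapy, so a sensible analyst would do the same for TTNT. The study is also descriptive, each cohort is analysed separately, and no between-cohort test is planned. Both points are fair, and the first points to the right repair. But no section assigns that start to TTNT, and each cohort's own median still needs a time zero.

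A reader might infer more than the documents support:

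- *That diagnosis is the stated origin of retrospective TTNT.* Section 7.1, under the consent heading, does abstract data "from the time of advCSCC diagnosis (i.e., index date) until the most recently documented visit, death, or lost to follow up". That sets the abstraction window and is not tied to TTNT. The shifts in step 4 of the working are therefore only illustrative.
- *That retrospective patients need not be unsuitable for curative treatment.* Section 8.1 defines locally advanced disease, for both cohorts, as not treatable with curative intent. At most a gap remains for metastatic patients.
- *That the cohort is selected on later non-use of cemiplimab, with a calculable bias.* That is one reading of the intention wording. Any percentage would depend on how many later next lines led to exclusion, and the documents do not give this.
- *That the intention wording should simply be deleted, or replaced by an analysis set cut at the approval date.* Deletion would make it easier for one patient to enter both cohorts. A new cut-off would depart from 14.2, and no listed CRF field records candidacy for curative radiation.

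**Conclusion.** The point holds as an internal contradiction. The only start defined for the primary variable is cemiplimab initiation, yet the variable is primary in a cohort of 200 patients treated otherwise. Taken literally, the retrospective half of the primary analysis has no result, and the 180 events assumed for it cannot arise. This rests on the protocol's text alone and needs no outside figure.

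The effect on precision does rest on assumptions. Under the exponential model and 10% censoring, the retrospective CI width at a 30-month median runs from 8.9 months (all treated) to 18.3 months (a quarter treated). No direction or size of bias between the cohorts is claimed.

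This should be corrected before the retrospective TTNT is analysed.

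**What to change.** 1. In 14.3.1.1 and the Section 9 CRF table, keep the cemiplimab start for the prospective cohort. For the retrospective cohort, define TTNT as the time from the start of the first documented systemic therapy for advCSCC to the start of the next systemic therapy (excluding BSC) or death. This matches the PFS start in 14.3.1.3.
2. State in 14.2 or 14.3.2.1 that retrospective patients without systemic therapy are described separately and do not enter the TTNT curve.
3. Restate the retrospective precision in the Synopsis and 14.1 for the number expected to have had systemic therapy.
4. Reconcile the intention wording in the Synopsis and 7.2 with 8.2 and 8.3. Say when intention is judged, how later cemiplimab counts for TTNT, and that no patient may enter both cohorts.

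**Cost:** an amendment to the wording. Section 9 already lists therapy line and start and stop dates. The price is a smaller retrospective TTNT set and a wider interval, for example about 12.7 instead of 8.9 months at a 30-month median if half of the patients were treated.
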